10.2. Study Drug Packaging and Labeling

The site will manage the distribution of TDF/FTC according to the CRC SOP. The study drug will be purchased from a local licensed pharmacy and stored in a secure, temperature controlled space.

10.3. Study Drug Storage

Study products will be stored at room temperature (15° - 30°C) (59° - 86°F) in a locked, secure, temperature monitored area in the clinic prior to dispensing.

10.4. Study Drug Preparation

These study products are ready to use and require no preparation other than packaging as described in Section 10.2.

10.5. Administration

Each of the doses is to be administered orally by the participant. In-clinic doses will include the dose on Day 1 (visit 2), Day 2 (visit 3) and Day 7 (visit 4). Participants will be asked to self-administer the other doses at home; participants may also come to the clinic to take their daily doses. The time of visits will be scheduled so it has been at least 24 hours since the participant’s last dose.

10.6. Study Drug Accountability

Dispensation of doses, doses taken by the participant, and returned unused doses will be recorded in the source documents.

10.7. Study Drug Handling and Disposal

All un-dispensed and returned study drug remaining at the end of the study will be recorded by the site and reconciled by the investigator. After reconciliation, any remaining study drug will be properly disposed of.

11. BIOANALYTICAL AND BIOCHEMICAL ASSESSMENTS

Blood, Urine and CV swabs will be taken to PK as detailed below in Tables 6 and 7.

Table 6: Example of Schedule for PK Samples for High Adherence Dosing Regimen (total of 14 doses)

Day of Week	Mon	Tues	Wed	Thurs	Fri	Sat	Sun	Mon	Tues	Wed	Thurs	Fri	Sat	Sun	Mon
Visit	2	3						4							5
Dose	1	2	3	4	5	6	7	8	9	10	11	12	13	14	
24 hour Post Dose Procedures	Blood, Urine, Vaginal Fluid	Blood, Urine, Vaginal Fluid						Blood, Urine, Vaginal Fluid							Blood, Urine, Vaginal Fluid
Day of Study	1	2	3	4	5	6	7	8	9	10	11	12	13	14	15

Table 7: Example of Schedule for PK Samples for Low Adherence Dosing Regimen (Total of 6 doses)

Day of Week	Mon	Tues	Wed	Thurs	Fri	Sat	Sun	Mon	Tues	Wed	Thurs	Fri	Sat	Sun	Mon
Visit	2	3						4							5
Dose	1		2		3			4		5		6			
24 hour Post Dose Procedures	Blood, Urine, Vaginal Fluid	Blood, Urine, Vaginal Fluid						Blood, Urine, Vaginal Fluid							Blood, Urine, Vaginal Fluid
Day of Study	1	2	3	4	5	6	7	8	9	10	11	12	13	14	15

12. ASSESSMENT OF SAFETY

12.1. Medical History

A medical history will be completed at Visit 1. Height, weight, and blood pressure will be measured.

As part of AE data collection, participant AEs will be assessed at each study visit starting after baseline sample collection at Visit 2 as applicable; participant report of symptoms will be documented and may result in follow-up assessments.

12.2. Physical Examination

A physical exam and pelvic exam will be performed at Visit 1 as necessary, based on participant history, signs and symptoms. If indicated, a directed physical exam will be performed at each study visit, with changes on physical exam documented.

12.3. Laboratory Assessments

12.3.1. Blood Samples

HIV and HBsAg tests will be performed at Visit 1. A serum creatinine will be performed to calculate a creatinine clearance at visit 1.

12.4. Pregnancy Screen

A pregnancy test is required at Visit 1. Note that participants must be protected from pregnancy as described in Section 7.1 in order to be eligible for study participation. A pregnancy test will be done at subsequent visits, if indicated by participant signs and symptoms.

13. ADVERSE AND SERIOUS ADVERSE EVENTS

13.1. Definition of Adverse Event (AE)

An AE is any untoward medical occurrence associated with the use of an investigational or approved product in humans, whether or not considered product related. An AE can therefore be any unfavorable and unintended sign (including an abnormal laboratory finding), symptom, or disease temporally associated with the use of an investigational product, whether or not considered related to the investigational product. Pre-existing events that increase in frequency or severity in nature during or as a consequence of use of an investigational product in human clinical trials will also be considered as AEs. Any AE with an onset date after the first date of study product administration is considered to be treatment-emergent.

All AEs with onset at or after baseline sampling, whether or not related to the study product, will be recorded in the study database.

According to 21 CFR 312.32 “IND Safety Reports” the following definitions of terms apply to AEs occurring in clinical studies involving drugs.

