6. INVESTIGATIONAL PLAN

6.1. Overall Study Design

This pilot, prospective, randomized study will screen approximately 20 healthy, non-pregnant, HIV negative, premenopausal women (aged 18-50) at EVMS who are not at risk of pregnancy and are at low risk for sexually transmitted infections (STIs) in order to have approximately 14 women complete all study visits. This study will examine the plasma, urine, and vaginal fluid from women in two dosing regimens of oral tablets: TDF/FTC (300/200 mg), 7 pills per week and TDF/FTC (300/200mg), 3 pills per week. Participants will be randomized to regimen as per the following schemata:

Table 3: Randomization Assignments

Regimen	N	Dose
Low Adherence (LA) Regimen	7	TDF/FTC (300/2200 mg), 3 pills/week, for a total of 6 ingested pills
High Adherence (HA) RRegimen	7	TDF/FTC (300/200 mg), 7 pills/week, for a total of 14 ingested pills

Participants will undergo the low adherence (LA) regimen or a high adherence (HA) regimen for two weeks, consisting of 5 visits.

Visit 1: At screening/enrollment, volunteers will be consented and undergo procedures to confirm they are eligible to continue in the study. Eligible participants will proceed to Visit 2.

Visit 2: Baseline blood, urine, and vaginal fluid will be collected. Participants will be randomized to dosing regimen and the first dose of TDF/TFC will be ingested in the clinic under direct observation. Participants will be instructed to take subsequent doses at home.

Dosing Contact: Participants will be sent reminder text messages to facilitate dosing occurring at the same time of day. Participants will text message the study coordinator to confirm ingestion of tablet. If the participant does not respond to a text within approximately 4 – 6 hours after it is sent, a reminder text will be sent.

Visits 3-5: Participants will return at 24 hours, 7 days, and 14 days after visit 2 for the pre-dose (for visits 3 and 4) collection of blood, urine, and vaginal samples.

Follow Up Contact: A final follow up site contact will be conducted approximately 1 – 2 weeks after the last visit to ask the participant about adverse events and concomitant medications. The participant will be exited unless there are symptoms that require follow up.

Table 4: Schedule of Evaluations

Single Dose Phase (EVMS only)				
	Visit 1 Screening	Visit 2 Baseline	Visit 3-5 24h, 7 days, and 14 days after Visit 2	Follow Up Contact
Informed consent	✓			
Review eligibility criteria, interval history	✓	✓		

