8.2. Visit 2: Baseline Pre-Dose Sample Collection

This visit will be scheduled for the early follicular phase of the menstrual cycle (for cycling women).

- An interval history will be collected.
- Eligibility criteria will be reviewed. If any lab tests reveal that the participant is not eligible, the visit should not proceed and the participant will not continue in the study.
- If indicated by signs or symptoms or history, a directed physical exam and/or urine pregnancy test will be performed. If pregnancy is diagnosed, the participant will be referred as necessary and will be discontinued.

- A vaginal swab for prostate specific antigen (PSA) will be obtained, if the PSA test indicates semen exposure, the visit will be re-scheduled.
- A urine sample will be obtained.
- Vaginal swabs will be obtained
- A blood sample (approximately 2 teaspoons) will be obtained.
- The participant will be randomized to the HA versus LA regimen and will take her first doses of TDF/FTC in the clinic under direct observation and the time of product ingestion will be recorded in the source document. The pill will be ingested after urine, vaginal and blood samples are obtained.
- The participant will confirm her contact information for the medication text reminder.
- Participants will be instructed to refrain from vaginal intercourse for 48 hours prior to visits 3 – 5.

8.3. Visits 3 – 5: 24 hours , 7 days, and 14 days after first dose

Visits 3, 4, and 5 will be scheduled for 24 hours, 7 days, and 14 days after initial dosing at Visit 2, respectively. The time of the visit will assure that it has been at least 24 hours since the participant's last dose of TDF/FTC. At each visit, the following procedures will be performed:

- The study staff will ask the participant if she followed the instructions from the previous visit, and ask about adverse events and concomitant medications.
- If indicated, a directed physical exam, pelvic exam and/or pregnancy test will be performed. If pregnancy is diagnosed, the participant will be referred as necessary and will be discontinued.
- Visits 4 and 5: Study staff will count the number of pills remaining and query the participant on compliance with her assigned dosing regimen.
- A vaginal swab for PSA will be obtained, if the PSA test indicates semen exposure, the participant will be reminded of the restrictions on vaginal intercourse, but the visit will proceed.
- A urine sample will be obtained.
- Vaginal swabs will be obtained

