13.3. Recording and Grading Adverse Events for Severity

Adverse events spontaneously reported by the participant and/or in response to an open question from the study personnel or revealed by observation will be recorded during the study at the clinical site. The AE term should be reported in standard medical terminology when possible. For each AE, the investigator will evaluate and report the date of onset, date of resolution, severity, relatedness, action

taken, serious outcome (if applicable), and whether or not it caused the patient to discontinue the study. Each AE will be graded for severity using the applicable DAIDS tables for grading the severity of adverse events (see Table 8), which can also be found at <http://rsc.tech-res.com/safetyandpharmacovigilance/>.

Table 8: Grading the Severity of Adverse Events

Adult and Pediatric AEs	http://rsc.tech-res.com/Document/safetyandpharmacovigilance/DAIDS_AE_Grading_Table_v2_NOV2014.pdf
Female Genital AEs	http://rsc.tech-res.com/Document/safetyandpharmacovigilance/Addendum_1_Female_Genital_Grading_Table_v1_Nov_2007.pdf
Rectal Grading Table	http://rcc.tech-res.com/docs/default-source/safety/rectal-tox-table-updates-05-11-2012.pdf?sfvrsn=6

For clinical AEs NOT identified in the DAIDS AE Grading Tables, the following scale (as listed in the DAIDS Table for Grading the Severity of Adult and Pediatric AEs) should be used to grade severity:

- Mild: Symptoms causing no or minimal interference with usual social and functional activities
- Moderate: Symptoms causing greater than minimal interference with usual social and functional activities
- Severe: Symptoms causing inability to perform usual social and functional activities
- Potentially Life-Threatening: Symptoms causing inability to perform basic self-care functions OR medical or operative intervention indicated to prevent permanent impairment, persistent disability, or death

It is important to distinguish between serious and severe AEs. Severity is a measure of intensity whereas seriousness is defined by the criteria under Section 13.1.3. An AE of severe intensity may not necessarily be considered serious.

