14.3. Analysis Populations

The population includes healthy, non-pregnant, HIV negative women. The analysis population will include all participants who undergo baseline genital/rectal sampling.

The Full Analysis Set (FAS) will consist of all subjects who are randomized and have at least one post-baseline assessment. The FAS will be used to summarize study disposition, baseline characteristics, and all non-safety endpoints.

Evaluation of safety endpoints will be conducted using the Treated Population (TP), consisting of women with at least one dose of product use. If all subjects in the TP have at least one post-baseline assessment, then the TP will be identical to the FAS.

All populations will be defined based on the adherence regimen assigned (HA versus LA).

Additional populations or refinements to these definitions, if needed due to unanticipated circumstances, will be described in the SAP or statistical report.

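### Section 13.1 defines treatment-emergent by a strict calendar-date rule, so an adverse event starting on Day 1 after the first tablet does not get the label

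*Combined protocol and SAP*

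**What the plan says.** The definition is in the combined protocol and SAP, Section 13.1: "Any AE with an onset date after the first date of study product administration is considered to be treatment-emergent". The paragraph that follows it sets a different starting point for data capture: "All AEs with onset at or after baseline sampling, whether or not related to the study product, will be recorded in the study database".

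Baseline sampling and the first dose fall at the same visit. Section 6.1 says that "the first dose of TDF/TFC will be ingested in the clinic under direct observation". Section 8.2 fixes the order, "The pill will be ingested after urine, vaginal and blood samples are obtained", and says that "the time of product ingestion will be recorded in the source document". Section 15.2 also asks the site to note the date and time of every dose taken in the clinic.

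For adverse events the time detail is coarser. Section 13.3 says that "the investigator will evaluate and report the date of onset, date of resolution, severity, relatedness", along with further items. A clock time of onset is not among them.

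Section 14.3 assigns safety evaluation to the Treated Population, meaning women who took one or more doses. Section 14.4 describes no adverse event table, and the term treatment-emergent appears only in Section 13.1.

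**The concern.** A treatment-emergent definition should separate events that could follow from the product from those that began before it was taken. Here the comparison is between two dates, and equality does not count. Gastrointestinal symptoms, which Section 8.5 gives as its example of what a participant should report, might begin within hours of the first tablet. On the written rule they would carry the same label as an event that began before the tablet was swallowed.

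If the study report tabulates treatment-emergent events by regimen, acute reactions to the first dose would be left out of that table even though they are in the database.

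**Working it through.** The plan states no figure for this point, so the check sets the rules side by side.

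Inputs:
- Label rule (Section 13.1): treatment-emergent if onset date > first-dose date.
- Recording rule (Section 13.1): recorded if onset is at or after baseline sampling.
- First dose: Day 1, Visit 2, after the samples (Section 8.2; Section 11, Tables 6 and 7).
- Time detail held: date and clock time for the first dose (Sections 8.2 and 15.2); date only for adverse event onset (Section 13.3).

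Applying the rules to each possible onset:

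| Onset | Recorded? | Label as written | Label if *on or after the date* | Label by date and time |
|---|---|---|---|---|
| Day 1, between sampling and tablet | Yes | No (Day 1 > Day 1 is false) | Yes | No if the time is known; yes if unknown |
| Day 1, after the tablet | Yes | **No** (Day 1 > Day 1 is false) | Yes | Yes |
| Day 2 or later | Yes | Yes | Yes | Yes |

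Three things follow.

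1. The second row is the error: an event after exposure does not get the label. No other section corrects it.
2. The wording is hard to read as shorthand for *on or after*. The recording rule in the same section says *at or after*, so both forms are used within a few lines. A programmer following the text would code a strict inequality.
3. The data as specified do not separate the first two rows. The dose time is available, but the onset time is not listed, so a date-and-time rule needs one more field.

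An illustration of what is at stake if a summary does use the label: assume the planned 7 women per regimen. Each woman whose only event began on Day 1 after the tablet would lower that regimen's treatment-emergent incidence by 1/7 = 14.3 percentage points. This is the weight of one woman and does not predict how many are affected. Section 9.4 specifies simple randomization, so the arms may not be exactly 7 and 7.

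**The case against.** The strongest reply is that nothing in the plan uses the label. The Treated Population in Section 14.3 decides which women are counted and places no filter on events. Serious events are captured from baseline (Section 13.1.3). Product holds turn on grade and relatedness (Section 13.5), and monthly reports turn on seriousness or relatedness (Section 19.3). The primary and secondary endpoints are tenofovir concentrations (Section 5.3). Because recording starts only at baseline sampling, nearly everything in the database is on-treatment anyway. All of this stands, and it limits the consequence. It does not make the definition right.

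A second reply is that the sentence says which events qualify and does not expressly say that the others do not. That is true of the grammar, but as the only definition it would be applied as an exclusion.

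A reader might go further than the documents allow in three ways:
- One might infer that Day 1 events are lost, or that the safety results will be understated in both arms. The events are kept, and understatement needs a summary that the plan does not name.
- One might size the gap by the first tablet's share of planned doses (one of 6 in the low adherence regimen, one of 14 in the high). Those are shares of doses, not of adverse events, and do not measure understatement.
- One might add that the Visit 2 dose is the only one observed in every woman. The example schedules in Tables 6 and 7 also place a dose at Visit 4 in both regimens, and Section 8.3 has that dose observed where it applies.

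**Conclusion.** The point holds as a fault in a stated rule: the text gives a definition, and that definition misclassifies first-dose reactions that start on the same day. The size is small. It is confined to events beginning on Day 1 after the tablet, it affects a label and not capture or safety action, and it reaches reported results only if the statistical report tabulates events by this definition. The number of events involved cannot be estimated from the documents.

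The conclusion rests on two assumptions: that the sentence would be applied literally, and that, as the only definition available, it would be treated as exhaustive. It does not bear on the concentration endpoints or on the comparison of the two assays.

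**What to change.** Replace the sentence in Section 13.1 with: *An AE with onset at or after the date and time of the first dose of study product is treatment-emergent; if the onset time on the first-dose date is unknown, the AE is counted as treatment-emergent.* In Section 13.3, add onset time to the items reported for any adverse event that starts on Day 1.

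The cost is one revised definition and one extra data field. The dose time is already collected, and no visit, sample or participant is added. The small downside is that a Day 1 event of unknown time that actually began between sampling and dosing would be counted as treatment-emergent. A plain *on or after the date* rule would need no new field, but it would count every event from that interval, including those whose timing could have been established.

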13.1.1. Suspected Adverse Reaction

A suspected adverse reaction is “any AE for which there is a reasonable possibility that the study product caused the event.” An AE is considered to be a suspected adverse reaction only if there is evidence to suggest a causal relationship between the study product and the AE. Examples of a causal relationship include:

- A single occurrence of an event that is uncommon and known to be strongly associated with product exposure (e.g., not necessarily applicable to this study, include angioedema, hepatic injury, Stevens-Johnson Syndrome)
- One or more occurrences of an event that is not commonly associated with product exposure, but is otherwise uncommon in the population exposed to the study product (e.g., tendon rupture)
- An aggregate analysis of specific events observed in a clinical trial (such as known consequences of the underlying disease or condition under investigation or other events that commonly occur in the study population independent of product exposure) that indicates those events occur more frequently in the product exposure group than in a concurrent or historical control group.

13.1.2. Adverse Reaction

An adverse reaction is any AE caused by the study product. Adverse reactions are a *subset* of suspected adverse reactions where there is reason to conclude that the product caused the event.

13.1.3. Serious Adverse Event (SAE) or Serious Suspected Adverse Reaction

An AE or suspected adverse reaction is considered “serious” if, in the view of either the investigator or the sponsor, it:

- Results in death

- Is immediately life-threatening
- Requires in-patient hospitalization or prolongation of existing hospitalization
- Results in persistent or significant disability or incapacity
- Results in a congenital abnormality or birth defect
- Is an important medical event that may jeopardize the patient or may require medical or surgical intervention to prevent one of the outcomes listed above

All SAEs starting from baseline until the last contact with the site, whether or not they are related to the study product, must be recorded on in the source documents and study database. Reporting of SAEs is outlined in Section 13.4.

13.1.4. Unexpected Adverse Event or Unexpected Suspected Adverse Reaction

An AE or suspected adverse reaction is considered “unexpected” if it is not listed in the drug packet insert, is not listed at the specificity or severity that has been observed. For example (not necessarily applicable to this study), under this definition, hepatic necrosis would be unexpected (by virtue of greater severity) if the package referred only to elevated hepatic enzymes or hepatitis. Similarly, cerebral thromboembolism and cerebral vasculitis would be unexpected (by virtue of greater specificity) if the package insert listed only cerebral vascular accidents. “Unexpected,” as used in this definition, also refers to AEs or suspected adverse reactions that are mentioned in the package insert as occurring with a class of drugs or as anticipated from the pharmacological properties of the drug, but are not specifically mentioned as occurring with the particular drug under investigation.

13.1.5. Serious and Unexpected Suspected Adverse Reaction

The sponsor must report any suspected adverse reaction that is both serious and unexpected. The sponsor must report an AE as a suspected adverse reaction only if there is evidence to suggest a causal relationship between the product and the AE as described above.

13.2. Relationship to Study Product

An Investigator who is qualified in medicine must make the determination of relationship to the investigational product for each AE. Relatedness is an assessment made by a study clinician of whether or not the event is related to the study agent. Degrees of relatedness will be categorized according to current DAIDS-approved guidelines. Per the Manual for Expedited Reporting of Adverse Events to DAIDS (Version 2.0, January 2010), the relationship categories that will be used for this study are:

- **Related:** There is a reasonable possibility that the AE is related to the study product(s)
- **Not related:** There is not a reasonable possibility that the AE is related to the study product(s)

